5.4.3 Muscle Related Adverse Events

Muscle related adverse events as reported on the general AE CRF will be summarized by SOC, PT, and maximum severity. All muscle related events and details associated with it including cause and location will be provided in a listing.

5.4.4 Adverse Events among Simvastatin 40mg Patients

TEAE and Serious TEAE by SOC and PT will be summarized by treatment group for patients who are on simvastatin 40mg or higher dose at any time during the study.

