### 11.1.6.3.5. Monitoring and Management of Elevated LDL-C

An adjunctive therapy plan is in place for those patients whose LDL-C values meet the protocol-defined LDL-C threshold criteria. Post-randomization, LDL-C results will be masked to investigators in order to maintain the blind; however, the following thresholds have been set to notify investigators and provide an opportunity to adjust the patient's standard of care regimen.

- Beginning at Week 24 (Visit T5) visit and for the duration of the study, the central laboratory will notify the investigator when the patient's LDL-C value is  $>170 \text{ mg/dL}$  (4.4 mmol/L) and  $\geq 25\%$  from the patient's baseline value at Week 0, (Visit T1)
- Upon receiving notification from the central laboratory that the patient has met or exceeded the threshold criteria for LDL-C, the investigator will initiate the following adjunctive therapy plan:
  - Patients will be scheduled to return to the clinic within 1 week for a repeat fasting blood lipid sample to confirm that the LDL-C value meets the threshold criteria
  - After confirming that the LDL-C value meets or exceeds the threshold criteria, the investigator will adjust the patient's lipid-lowering treatment regimen per standard-of-care and local practice, with the exception of simvastatin *at doses  $\geq 40 \text{ mg/day}$*  and the fibrate, gemfibrozil. The patient's LDL-C will be re-evaluated at the next scheduled clinic visit as defined in the Schedule of Visits ([Appendix 1](#)).
  - The initiation of *any new or dose changes of any existing lipid-lowering treatment* will be documented on the eCRF as a concomitant medication with the associated start date
  - *Patients who have their lipid-lowering medications modified, including new medications or dosage changes to existing medications, should return to the clinic in 4 weeks after the modification to their lipid-lowering treatment for a routine safety laboratory assessment. Additional safety laboratory assessments may be conducted at the investigator's discretion. Patients receiving an average daily dose of simvastatin 40 mg based on lipid-lowering treatment modification, should adhere to the additional safety visits as described in [Sections 10.2.5](#) and [10.2.6](#).*
  - Adjunctive therapy medications will not be provided by the sponsor

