3.2.1 Adverse Events

The evaluation of AEs will include only incidence of treatment-emergent AEs (TEAEs), defined as AEs that begin or worsen after the first dose of IMP until 30 days after last dose of IMP. Clinical endpoints will be collected and adjudicated by an independent

Confidential

Page 7 of 33

Clinical Events Committee (CEC). Clinical endpoints will also be reported as SAEs. Adverse events of special interest (AESI) will further be examined (See Section 5.4.2 for more information).

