5.2.3 Patient Disposition

The number of patients screened, randomized and included in each analysis population, along with study completion status, will be summarized by treatment group as well as overall. In addition, the number of patients who withdraw from the study and withdraw from IMP will be summarized by discontinuation reason.

Patient disposition will also be summarized for patients who are on simvastatin 40 mg/day or higher dose at any time during the study. The identification of these patients will be based on the concomitant statin medication use.

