5.2.8 Prior and Concomitant Medications

Prior medications are defined as medications that ended prior to the initiation of double-blind IMP. Concomitant medications are defined as medications that were ongoing at the time of double-blind IMP initiation or new medications that started post double-blind IMP initiation and within 30 days following the date of the last dose of IMP.

Medications, including prior statin medications, will be coded using WHO Drug (March, 2015, or later). The use of prior or concomitant medications will be summarized by treatment group, as well as overall, for the safety population according to Anatomical Therapeutic Chemical (ATC) class and coded medication name. Statin medications will be summarized separately. Prior and concomitant medications will be listed for each patient.

Number of patients receiving additional (post-randomization) adjunctive lipid-modifying therapy will be identified by medication class and will be summarized by the reasons for their additional treatment (hyperlipidemia or. hypertriglyceridemia) per concomitant medication CRF.

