5.4.6.2 Musculoskeletal Safety

CK levels will be summarized by the value and change from baseline in the value, by treatment group and visit as well as baseline eGFR category. In addition, the number and percent of patients with abnormal CK values ($> 5 \times \text{ULN}$, $> 10 \times \text{ULN}$) will be summarized for overall safety population and patients who were on simvastatin 40mg or higher dose at any time during the study. These summaries of patients with abnormal CK will be performed overall, normal baseline CK, and abnormal baseline CK.

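### The simvastatin 40 mg safety subgroup is defined by use at any time during the study, so patients can enter it after randomisation and events from before that dose are counted

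*SAP*

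**What the plan says.** SAP 5.4.4 gives treatment-emergent and serious treatment-emergent events by treatment group "for patients who are on simvastatin 40mg or higher dose at any time during the study". The same set is used for disposition (5.2.3), demographic and baseline characteristics (5.2.4), ALT/AST/TB abnormalities (5.4.6.1) and CK abnormalities (5.4.6.2, "overall safety population and patients who were on simvastatin 40mg or higher dose at any time during the study").

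On membership, SAP 5.2.3 says "The identification of these patients will be based on the concomitant statin medication use". SAP 5.2.8 counts as concomitant any drug ongoing at the first dose of IMP, and also "new medications that started post double-blind IMP initiation and within 30 days following the date of the last dose of IMP".

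On counting, SAP 3.2.1 has treatment-emergent events "defined as AEs that begin or worsen after the first dose of IMP until 30 days after last dose of IMP". SAP 5.4.6 considers every laboratory value after baseline for the abnormality summaries. Neither rule refers to simvastatin start or stop dates.

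Protocol 11.1.6.3.5 describes an LDL-C-triggered change of lipid-lowering therapy that operates "Beginning at Week 24 (Visit T5) visit and for the duration of the study". It says "Patients receiving an average daily dose of simvastatin 40 mg based on lipid-lowering treatment modification, should adhere to the additional safety visits". The same section excludes simvastatin at 40 mg/day or more from the permitted changes, and Protocol 8.2.2 prohibits that dose during the study.

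**The concern.** A subgroup compared by arm should be fixed before treatment can influence who belongs to it. The subgroup variables in SAP 5.2.5 are all baseline characteristics; this set is not. A patient can join it through a statin change prompted by that patient's own LDL-C on study. SAP 5.3 hypothesises a larger reduction on bempedoic acid, so placebo patients would be expected to meet the trigger more often. Late entry could then differ by arm.

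Once a patient is in, all treatment-emergent events count, including those before simvastatin 40 mg was started or after it was stopped. For the laboratory tables there is a further gap. The SAP's summary of changes says that patients on 40 mg/day or more were withdrawn from study treatment under Amendment 5. Protocol 10.3.1 asks withdrawn patients to continue visits, with safety laboratories. Their CK and liver values from long after the last dose of IMP would stay in the subgroup tables, and this applies to baseline users too.

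The primary endpoint is safety. Protocol 10.2.5.1 and 10.2.6.1 added visits specifically to watch CK and liver tests in patients on this dose. Tables that mix in time without the dose, or without IMP, can dilute or distort what they show.

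**Working it through.** The documents give no figure for this subgroup, so there is none to reproduce. The check is of definitions, followed by an illustration of size.

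**Step 1, membership.** Any-time use (SAP 5.4.4), found from concomitant records (5.2.3) that run to 30 days after the last IMP dose (5.2.8), admits three kinds of patient:
- users of 40 mg at entry, since Protocol 7.2 excludes only average daily doses above 40 mg;
- patients who reach 40 mg while on IMP;
- patients who first take 40 mg within 30 days after stopping IMP.

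The last two are defined by information that arises after randomisation. Because entry excludes doses above 40 mg, members above 40 mg can arise only after randomisation or through an eligibility deviation.

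**Step 2, counting.** The event window runs from first IMP dose to last IMP dose plus 30 days (SAP 3.2.1). For entry users, no time before exposure is counted. For on-study starters, all events before the start are counted. For those who start only after the last dose, every event on IMP is counted with no concurrent dosing. Laboratory values have no end limit at all (SAP 5.4.6).

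**Step 3, the route.** The LDL-C rule starts at the Week 24 visit, Day 169 ± 7, with a repeat sample within 1 week (Protocol Appendix 1 and 11.1.6.3.5). Start days from 162 to 183 cover that route at its earliest. Day 253 is the Week 36 visit.

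**Step 4, share of the window before the dose, per late starter.** With start day d and window length T, share = (d − 1)/T. T is 365 days to Week 52, or 365 + 30 = 395 with the tail.

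| Start day | T = 365 | T = 395 |
|---|---|---|
| 162 | 161/365 = 44% | 161/395 = 41% |
| 183 | 182/365 = 50% | 182/395 = 46% |
| 253 | 252/365 = 69% | 252/395 = 64% |

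**Step 5, share of the subgroup's at-risk time.** If late starters are a fraction f of the subgroup, the share is f × (d − 1)/T. The documents do not give f, so a range is assumed, with a constant event rate and equal follow-up. The low end uses d = 162, T = 395; the high end uses d = 253, T = 365.

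| f (assumed) | Low | High |
|---|---|---|
| 5% | 2.0% | 3.5% |
| 10% | 4.1% | 6.9% |
| 25% | 10.2% | 17.3% |
| 50% | 20.4% | 34.5% |

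**The case against.** The strongest reply is that late starters are few. The section that mentions "Patients receiving an average daily dose of simvastatin 40 mg based on lipid-lowering treatment modification" also bars simvastatin at 40 mg/day or more as adjunctive therapy, and Protocol 8.2.2 prohibits it on study. The amendment summaries show the adjunctive route to 40 mg open on protocol only between Amendment 3 (28 July 2016) and Amendment 5 (10 May 2017). It needed a confirmed LDL-C above 170 mg/dL and at least 25% from baseline, at Week 24 or later, in a patient already on a maximally tolerated statin. Visits T4.1 and T4.2, at Weeks 16 and 20, precede that route, so the extra visits were built chiefly for patients already on the dose. This stands, and it limits the size. It does not remove the definition: off-protocol use, and use begun after IMP has stopped, are still captured.

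A reader might also infer that the SAP presents these events as events on the combination, or plans an interaction analysis. It does neither. Section 5.4.4 is headed as events among simvastatin 40 mg patients, the summary of changes says the analyses were added to understand this group further, and no test or interaction estimate is planned. An inclusive set is a natural first choice for that purpose.

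Finally, all adverse events and all concomitant medications are listed by patient, so timing can be reconstructed case by case. That is true, but the tables themselves would not show it.

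**Conclusion.** The point holds. As defined, the subgroup rests on a variable measured after randomisation. Its by-arm tables are not protected by randomisation, and they include events and laboratory values from before simvastatin 40 mg was taken. The CK and liver tables also keep values from after IMP withdrawal.

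The size is not known and is probably small. Per late starter, 41 to 50% of the window precedes the dose for a start around Week 24, and 64 to 69% for a start at Week 36. At subgroup level the share depends on an unknown fraction of late starters: about 2 to 7% if they are 5 to 10% of members. These shares assume a constant event rate and equal follow-up. The documents do not support a claim that the arms are materially unbalanced by late entry; they show only that the definition allows it. The tables are descriptive, so no test and no sample size is affected.

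Separately, the protocol contradicts itself. The synopsis and 7.2 exclude only doses above 40 mg at entry. Section 8.2.2 prohibits 40 mg/day or more. The synopsis and 11.1.6.3.5 bar that dose as adjunctive therapy yet set visits for patients who reach 40 mg through a treatment change. These passages must be reconciled.

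**What to change.** In SAP 5.2.3, 5.2.4, 5.4.4, 5.4.6.1 and 5.4.6.2:

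- Define the main subgroup as average daily simvastatin of 40 mg or more on the latest statin record before randomisation. Appendix 3 already derives average daily statin dose from that record.
- Keep the treatment-emergent window for adverse events, and apply the same window, to 30 days after the last IMP dose, to the subgroup's CK and ALT/AST/TB tables.
- Show patients who first reach 40 mg after randomisation in a separate table or listing, with event timing relative to simvastatin start and stop.
- Make any count restricted to time on simvastatin 40 mg supplementary, with a stated lag after simvastatin is stopped and with person-time rates. Without a lag, a CK or liver elevation found just after stopping would be lost; without person-time, the percentages would not be comparable.

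The cost is SAP wording and reuse of an existing derivation. The main subgroup becomes slightly smaller, but no case is lost because later starters are shown separately. The subgroup laboratory tables will use a narrower window than the overall safety population tables beside them, so a footnote is needed.

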5.4.5 Clinical Cardiovascular Endpoints

Clinical cardiovascular endpoints will be monitored and adjudicated by an independent blinded expert CEC for this study and other ongoing studies the ETC-1002 program. Adjudicated clinical endpoints that are treatment-emergent will be summarized by event type and treatment group. All events will be provided in a listing. Additional details regarding clinical endpoints and clinical endpoint definitions will be included in CEC charter.

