#### Renal Safety

Baseline estimated glomerular filtration rate (eGFR) will be summarized by treatment group for actual value and for baseline eGFR categories. Shift tables of eGFR category from baseline over the study, will be provided by treatment group. Shift tables of urine protein (negative/positive) from baseline over the study, will be provided by treatment group. Values of CK over the study will be summarized by treatment group and by baseline eGFR category. Finally, muscle-related AEs will be summarized by treatment group and by baseline eGFR category.

Clinical Endpoints

*Clinical endpoints* will be monitored and adjudicated by an independent blinded expert CEC for ongoing studies the ETC-1002 program. Adjudicated *clinical endpoints* will be summarized by event type and treatment group. Additional details regarding *clinical endpoints* and *clinical endpoint* definitions will be included in CEC charter.

Neurocognitive Events

Neurocognitive events will be identified and evaluated by routine safety monitoring of PE findings and AEs. Summarization of neurocognitive events will occur using prespecified Medical Dictionary for Regulatory Activities (MedDRA) terms and will be performed by SOC, severity, and relationship to study drug for each treatment group

Key Efficacy Endpoints

*Percent change from baseline to Week 12 or Week 24 in LDL-C, non-HDL-C, TC, apoB, and hs-CRP will be analyzed using analysis of covariance (ANCOVA), with treatment and randomization strata (patient's CV risk and baseline statin dose) as factors and respective baseline value as a covariate. The FAS will be used. Missing data for these endpoints will be imputed using multiple imputation taking account for treatment adherence.*

Other Efficacy Endpoints

*LDL-C, HDL-C, TG, TC, non-HDL-C, hs-CRP, and apoB values at other time points will be summarized and analyzed similarly to the key lipid endpoints. In addition, a summary using the FAS, excluding patients who received additional lipid-lowering therapy by that time point (by Week 24 for the Week 24 time point; by Week 52 for the Week 52 time point), will be provided. For both summaries, only observed case data will be used (no imputation for missing data).*

Additional post-randomization adjunctive lipid-modifying therapy

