## 10.3. Subject Withdrawal Criteria

### 10.3.1. Early Withdrawal from the Study

Patients must remain in the study until the last scheduled visit at Week 52 (Visit T7) to be considered as having completed participation in the study.

Patients who withdraw from IMP prior to Week 52 (Visit T7) for any reason will be asked to continue to be followed for safety assessments, *including basic fasting lipids*, at clinic visit following the protocol-specified visit schedule (see [Appendix 1](#)). The patient must provide consent to be followed in the study after withdrawing from IMP treatment. Protocol procedures to be completed for patients who consent will include those specified at each visit as noted in Schedule of Events (see [Appendix 1](#)).

*Patients who temporarily withdraw from IMP prior to Week 52 (Visit T7) for any reason may restart IMP providing that 1) the patient and the investigator are in agreement regarding this course of action, 2) the patient has been off of IMP for 4 weeks or less; and 3) IMP can be started as soon as possible. For cases where the patient has been off of IMP for more than 4 weeks, the investigator must contact the medical monitor for approval prior to restarting IMP.*

Patients who do not provide consent to continue to return to the clinic for safety assessments will be asked to participate in phone calls from the site at protocol-specified visits (see [Appendix 1](#)), or at a minimum at 52 weeks, to collect information on AEs, *concomitant medications*, and current health status. The patient must provide consent to be contacted by phone by site personnel for the purposes of assessing current AEs and current health status.

The patient's decision to participate in the clinical study is voluntary. Patients may refuse to continue in the study and/or withdraw from participation in this study at any time, for any reason, specified or unspecified, and without penalty or loss of benefits to which the patient is otherwise entitled.

It is the right and duty of the Investigator to interrupt the treatment of any patient whose health or well-being may be threatened by continuation in this study. Such patients should be withdrawn from the study and should not be continued under a modified regimen.

Patients who are withdrawn from the study may not re-enter. The reasons for withdrawal from this study may include:

- Patient's withdrawal of consent
- Failure to comply with the protocol
- Lost to follow-up

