### **11.2.7. Treatment-Emergent Adverse Events**

TEAE are defined as AEs that begin or worsen after the first dose of study drug.

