Route of Administration:	Oral, daily (once every 24 hours, at approximately the same time each day), with or without food	Oral, daily (once every 24 hours, at approximately the same time each day), with or without food
Physical Description:	Oval, white to off-white film-coated tablet debossed with “ABC” on one face and debossed with “000” on the opposite face	Oval, white to off-white film-coated tablet debossed with “ABC” on one face and debossed with “000” on the opposite face
Manufacturer (Fill/Finish):	Norwich Pharma Services [name] AND: Patheon [name]	Norwich Pharma Services [name] AND: Patheon [name]

^a A 100-day supply of IMP will be included in the 100-count bottle and a 35-day supply of IMP will be included in the 35-count bottle.

Randomized patients will continue in the study until they have completed Week 52 (Visit T7). Randomized patients will return for clinic visits at Week 4 (Visit T2), Week 8 (Visit T3), Week 12 (Visit T4), Week 24 (Visit T5), Week 36 (Visit T6), and Week 52 (Visit T7).

Patients on an average daily dose of simvastatin 40 mg will be scheduled for the additional Visit T4.1 (Week 16) and T5.1 (Week 28) for clinical safety laboratory evaluations specifically to monitor changes in creatine phosphokinase (CPK) and liver function tests (LFTs). On Visit T4.2 (Week 20, phone only), and T5.2 (Week 32, phone only), these patients will be monitored for AE and SAE occurrences.

Patients who withdraw from investigational medicinal product (IMP) treatment will be asked to continue to be followed for safety using the protocol-specified visit schedule and

procedures. For details of study assessments, see Appendix 1: Schedule of Events (Patient Visit Schedule).

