4.6 Changes from Protocol Planned Analyses

- 1) Additional subgroup analysis and sensitivity analyses are proposed and described in this SAP.
- 2) It is clarified in the SAP that study objectives are supported by both primary safety and primary efficacy endpoints.
- 3) Multiplicity adjustment amongst efficacy endpoints is implemented and described in this SAP.

5 Statistical and Analytical Plans

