5.4.1 Adverse Events (AEs)

AEs will be coded using the Medical Dictionary for Regulatory Activities (MedDRA) Version 18.1 or later and will be categorized by system organ class (SOC) and preferred term (PT). Patients with AEs that are ongoing at study completion or study withdrawal must be followed until resolution or for 30 days after the last study visit, whichever comes first. Summary tables will focus on TEAEs; however, listings will include all AEs (with non-TEAEs flagged).

In summary tables, TEAEs will be counted as “Not Related” if relationship to IMP was recorded as ‘Not Related’ or ‘Unlikely’. Events will be counted as “Related” if relationship to IMP was recorded as ‘Possible’, ‘Probable’, ‘Definite’ or if relationship to IMP is missing.

The severity of the AE will be characterized as mild, moderate, or severe, to the following definitions:

- Mild: Events are usually transient and do not interfere with the patient’s daily activities
- Moderate: Events introduce a low level of inconvenience or concern to the patient and may interfere with daily activities
- Severe: Events interrupt the patient’s usual daily activity, are incapacitating with inability to do usual activities, or significantly affect clinical status and warrant intervention and/or close follow-up

Overviews of TEAEs will include total number of TEAEs and patient incidence of TEAE, TE SAE, related TEAE, related TE SAE, AESI, withdrew due to TEAE, Fatal Confidential

TEAE. Individual TEAE summary will be presented by treatment group containing the following counts and percentages for:

- patients with TEAEs
- patients with TEAEs by PT
- patients with TEAEs by SOC, PT and maximum severity
- patients with treatment-related TEAEs
- patients with treatment related TEAEs by PT
- patients with treatment related TEAEs by SOC, PT and maximum severity
- patients with treatment-emergent serious adverse events (TE SAEs)
- patients with TE SAEs by PT
- patients with TE SAEs by SOC, PT and maximum severity
- patients with treatment-related TE SAEs
- Fatal AEs by SOC and PT
- withdrawal from IMP due to TEAEs

Patient incidence (percent of patients experiencing the AE) will be provided for overall TEAE, treatment related TEAE, TE SAE, treatment related TE SAE, and AESI.

The TEAE, related TEAE, TE SAE, and AESI summaries by SOC and PT and maximum severity will be provided for relevant subgroups described in 5.2.5 with the exception of baseline LDL category.

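### Adjudicated cardiovascular endpoints and deaths are tabulated by arm only to 30 days after the last IMP dose, and the SAP does not declare this narrowing

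*SAP*

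**What the plan says.** **The by-arm table.** SAP 5.4.5: "Adjudicated clinical endpoints that are treatment-emergent will be summarized by event type and treatment group". The section then places all events in a listing.

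**The window.** SAP 3.2.1 holds the SAP's only definition of treatment-emergent: TEAEs are "defined as AEs that begin or worsen after the first dose of IMP until 30 days after last dose of IMP". The same subsection introduces the CEC-adjudicated endpoints and says they are also reported as SAEs.

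**Follow-up after stopping IMP.** Under SAP 4.2, patients who come off IMP "treatment will be asked to continue to be followed for safety using the protocol-specified visit schedule". Under Protocol 10.3.1, those who withdraw from IMP before Week 52 "for any reason will be asked to continue to be followed for safety assessments". Protocol 11.3 collects SAEs until 30 days after study completion or discontinuation, so the clock does not run from the last dose.

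**The protocol's analysis.** The synopsis (Statistical methods, Clinical Endpoints) says adjudicated clinical endpoints "will be summarized by event type and treatment group", with no treatment-emergent condition. Protocol 11.2.7 sets no end date: "TEAE are defined as AEs that begin or worsen after the first dose of study drug".

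**Declared changes.** SAP 4.6 lists three. The first is "Additional subgroup analysis and sensitivity analyses are proposed and described in this SAP"; the other two concern the roles of the safety and efficacy endpoints and multiplicity among efficacy endpoints. The SAP's own Summary of Changes does not mention the window either.

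**Deaths.** Protocol 12.5 promises a summary of deaths by treatment group. SAP 5.4.1 lists "Fatal AEs by SOC and PT" among the individual TEAE summaries.

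**The concern.** The primary objective is long-term safety against placebo. The adjudicated endpoints, including CV and non-CV death, are among the most serious outcomes the trial collects. A table cut at last dose plus 30 days conditions on when a patient stopped IMP, which happens after randomization and is sometimes caused by a health event. Protocol 11.1.6.3.2, for example, withdraws patients from IMP for acute renal failure and asks them to stay in follow-up. Amendment 5 also took the simvastatin 40 mg group off IMP (SAP Summary of Changes, item 10), with safety follow-up for those who consent (Protocol Appendix 10).

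For such patients the trial gathers and adjudicates later events, but a reader comparing arms would have to count them by hand from a listing. The SAP supersedes the protocol on analysis, so the narrower rule would govern without having been declared as a change.

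**Working it through.** **1. Does the limit follow from the text?** Section 5.4.5 tabulates treatment-emergent events and lists all events, so it expects some adjudicated events to fall outside the table. No other window is defined in the SAP. A patient still on IMP at Week 52 has a window that runs to about 30 days after the last visit, which roughly matches the end of SAE collection. Only early IMP stoppers lose tabulated time.

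**2. Reproduce the plan's exposure figures (SAP 4.4).** N × (1 − dropout):
- ETC-1002: 1300 × 0.925 = 1202.5 and 1300 × 0.90 = 1170 (printed 1,202 and 1,170)
- Placebo: 650 × 0.925 = 601.25 and 650 × 0.90 = 585 (printed 601 and 585)

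They reproduce.

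**3. Time outside the window.** Assume that all planned dropout is IMP discontinuation, spread evenly within each half-year, and that every stopper is followed to day 364. For a stop on day t, the days outside are max(0, 364 − (t + 30)).
- 7.5% stopping on days 0 to 182: mean 334 − 91 = 243.0 days; 0.075 × 243.0 = 18.2
- a further 2.5% stopping on days 182 to 364: mean 152² / (2 × 182) = 63.5 days; 0.025 × 63.5 = 1.6
- total 19.8 days per patient; 19.8 / 364 = 5.4%
- ETC-1002: 1300 × 19.8 / 365.25 = 70.5 patient-years; placebo: 650 × 19.8 / 365.25 = 35.3; together 105.8

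**4. Expected events outside the table, both arms, to Week 52.** The documents give neither an event rate nor the fraction followed off IMP, so both are assumed.

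| Stoppers followed | Patient-years outside | 0.5% per year | 3% per year | 5% per year |
|---|---|---|---|---|
| 100% | 105.8 | 0.5 | 3.2 | 5.3 |
| 50% | 52.9 | 0.3 | 1.6 | 2.6 |
| 25% | 26.4 | 0.1 | 0.8 | 1.3 |
| 0% | 0 | 0 | 0 | 0 |

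For scale, the whole trial at 3% would yield 1950 × 364 / 365.25 × 0.03 = 58.3 events. The 3.2 events in the first row split as about 2.1 on ETC-1002 and 1.1 on placebo.

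**5. What could raise the figure.**
- Counting SAEs to 30 days after completion (day 394) changes the means to 273.0 and 91.0 days: 0.075 × 273.0 + 0.025 × 91.0 = 22.75 days per patient, or 81.0 + 40.5 = 121.5 patient-years.
- The number of simvastatin 40 mg patients withdrawn from IMP is not given. If they are additional to planned dropout, each 1% of enrolment (19.5 patients) stopped at day 182 and followed adds 19.5 × (364 − 212) / 365.25 = 8.1 patient-years.
- If IMP discontinuation were twice the planned rate (20% by 12 months), the time outside doubles to 141.0 + 70.5 patient-years, about 10.9% of planned time.

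**The case against.** **The window is inferred.** Section 5.4.5 does not state the 30-day limit; it comes from a definition written for adverse events, and the CEC charter is not available to check. That is true. But the endpoints are reported as SAEs, the definition stands in the subsection that introduces them, and the SAP offers no other. If full follow-up was intended, one sentence would settle it.

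**The protocol already restricts AE summaries to TEAEs.** Also true (Protocol 12.5), and part of that section is redacted, so the contrast for adjudicated endpoints rests on the synopsis. The protocol's TEAE definition still has no end date, so even on this reading the SAP has added the 30-day stop without saying so.

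**Nothing is lost, and deaths are covered.** All adjudicated events are listed, and the fatal-AE table may well cover every death: the overview names fatal TEAEs, while this table says only AEs. But a listing gives no count by arm. The fatal-AE table sits under the TEAE summaries, so its scope is unclear, and it is organized by MedDRA term and not by adjudicated CV or non-CV cause.

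**The effect is small, and an on-drug window is a legitimate analysis.** Both stand. If planned dropout means leaving the study altogether, the number approaches zero. The DMC review and the program-level aggregation (Protocol 11.5 and 11.6) may use full follow-up; the documents do not say. These points limit the importance of the gap but do not justify having only the restricted by-arm view.

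**Conclusion.** The concern holds. As written, the SAP gives a by-arm summary of adjudicated MACE and non-MACE endpoints only to 30 days after the last IMP dose, although later events are collected and the protocol synopsis set no such limit. This is an undeclared narrowing; the on-drug analysis is not itself invalid.

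On the planned dropout, between 0 and 5.4% of patient-time falls outside the window to Week 52, giving 0 to about 5 events at assumed annual rates up to 5%. The upper end assumes that all dropout is IMP-only and that every stopper is followed. Simvastatin 40 mg patients taken off IMP could add to it by an unknown amount. The number is probably small and no direction is claimed. It should be corrected because a few events can matter for individual types such as CV death, and because the omitted patients include some who stopped for health reasons.

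**What to change.** 1. In SAP 5.4.5 keep the treatment-emergent table and add a by-arm summary of all adjudicated MACE and non-MACE endpoints, including CV and non-CV death, from first dose to the end of study follow-up regardless of IMP status. This is the substantive change.
2. In SAP 5.4.1 state that the fatal-AE table covers all deaths to the end of follow-up.
3. In SAP 4.6 record the 30-day window as a change from the protocol.

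Descriptive risk differences and relative risks with 95% confidence intervals for these endpoints and deaths would be a useful extra, but the correction does not depend on them.

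The cost is SAP wording and one or two tables from data already collected. The downside is that off-drug events dilute a purely on-drug comparison; the retained treatment-emergent table still shows that comparison.
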